9.1.8 Investigators Reporting of AEs

Information on all grade 3 AEs should be recorded on the appropriate CRF. All clearly related signs, symptoms, and results of diagnostic procedures performed because of an AE should be grouped together and recorded as a single diagnosis. If the AE is a laboratory abnormality that is part of a clinical condition or syndrome, it should be recorded as the syndrome or diagnosis rather than the individual laboratory abnormality. Each AE will also be described in terms of duration (start and stop date), severity, association with the study product, action(s) taken, and outcome. Guidelines regarding reporting and limits will be provided to all participating centers.

9.1.9 Serious Adverse Event Reporting

Investigators Reporting of SAEs

Any AE grade 4 that meets a protocol-defined criterion as a SAE must be submitted immediately (within 24 hours of site awareness) in the eCRF. The designated Medical Monitor will review and assess the SAE for regulatory reporting and potential impact on study subject safety and protocol conduct. The Medical Monitor will be available 24/7 on a designated mobile number.

Regulatory Reporting of safety data

All Suspected Unexpected Adverse Reactions (SUSAR) have to be reported, within the legal timeframe, by the sponsor to the National Competent Authority of the Member State concerned. The timelines for expedited initial reporting (day 0) starts as soon as the information containing the minimum reporting criteria has been received by the sponsor. For fatal and life-threatening SUSARs the sponsor should report at least the minimum information as soon as possible and in any case no later than seven days after being made aware of the case. SUSAR which are not fatal and not life-threatening are to be reported within 15 calendar days. If significant new information on an already reported case is received by the sponsor, this information should be reported as a follow-up report within 8 days after being made aware of the relevant complementary information.

In addition, any serious unexpected adverse reaction that is life-threatening (e.g. anaphylaxis, Stevens-Johnson syndrome, aplastic anaemia, or any other life-threatening condition in the opinion of the investigator) must be reported through the WHO study website within 24 hours (SOP 9).

Once a year throughout the clinical trial, the sponsor should submit to the national competent authority and the Ethics Committee of the Member States, an annual safety report.

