9.1.2 Definition of Serious Adverse Event (SAE)

An SAE is defined as “An AE or suspected adverse reaction is considered serious if, in the view of either the investigator or the sponsor, it results in any of the following outcomes:

- Death,
- a life-threatening AE,
- prolongation of existing hospitalization,
- a persistent or significant incapacity or substantial disruption of the ability to conduct normal life functions,
- or a congenital anomaly/birth defect.
- important medical events

Important medical events that may not result in death, be life-threatening, or require hospitalization may be considered serious when, based upon appropriate medical judgment, they may jeopardize the patient or subject and may require medical or surgical intervention to prevent one of the outcomes listed in this definition

“Life-threatening” refers to an AE that at occurrence represents an immediate risk of death to a subject. An event that may cause death if it occurs in a more severe form is not considered life-threatening. Similarly, a hospital admission for an elective procedure is not considered a SAE. All SAEs, as with any AE, will be assessed for severity and relationship to study intervention. All SAEs will be recorded on the appropriate SAE CRF. All SAEs will be followed through resolution or stabilization by a licensed study physician.

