9.1.5 Severity of Adverse Events

AEs will be graded according to the following definitions:

- Mild (Grade 1): Events that are usually transient and may require only minimal or no treatment or therapeutic intervention and generally do not interfere with the subject’s usual activities of daily living.
- Moderate (Grade 2): Events that are usually alleviated with additional specific therapeutic intervention. The event interferes with usual activities of daily living, causing discomfort but poses no significant or permanent risk of harm to the research subject.
- Severe (Grade 3): Events interrupt usual activities of daily living, or significantly affects clinical status, or may require intensive therapeutic intervention. Severe events are usually incapacitating.
- Life-threatening (Grade 4): Urgent intervention indicated.

AEs characterized as intermittent require documentation of onset and duration of each episode. The start and stop Duration of each reported AE will be recorded on the appropriate CRF. Changes in the severity of an AE will be documented to allow an assessment of the duration of the event at each level of intensity.

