9.1.7 Time Period and Frequency for Event Assessment and Follow-Up

For this study, all Grade 3 and 4 AEs, Grade 1 and 2 AEs for Remdesivir occurring while administration or within the first hour and all SAEs occurring from the time the informed consent is signed through three months follow-up will be documented, recorded, and reported.

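### The 24-hour site deadline covers only grade 4 SAEs, and the SAE list omits new admission although the same section presupposes it

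*Protocol*

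**What the plan says.** **Deadline.** Protocol 9.1.9 states the investigator's deadline for submission in the eCRF: "Any AE grade 4 that meets a protocol-defined criterion as a SAE must be submitted immediately (within 24 hours of site awareness". Review by the Medical Monitor comes next in that section. The severity scale in 9.1.5 has four grades, the highest being "Life-threatening (Grade 4): Urgent intervention indicated".

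**Definition.** Section 9.1.2 lists six grounds for seriousness: death, a life-threatening event, "prolongation of existing hospitalization", incapacity, birth defect and important medical events. None refers to grade. The section also says "Important medical events that may not result in death, be life-threatening, or require hospitalization may be considered serious" and that "a hospital admission for an elective procedure is not considered a SAE".

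**Recording.** Section 9.1.2 requires that "All SAEs will be recorded on the appropriate SAE CRF". Section 9.1.7 requires that "all SAEs occurring from the time the informed consent is signed through three months follow-up will be documented, recorded, and reported", together with all grade 3 and grade 4 AEs. Section 9.1.8 tells investigators: "Information on all grade 3 AEs should be recorded on the appropriate CRF". Section 9.1.1 likewise names only grade 3.

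**Use.** The opening of section 9 makes the sponsor responsible for deciding which SAEs are SUSARs, and 9.1.3 allows any SAE to be one. Section 9.1.9 gives the sponsor seven days for fatal and life-threatening SUSARs and 15 calendar days for the others, counted from receipt of the minimum information. Section 10.5.3 analyses death through three months, SAEs, discontinuation of infusions and severe AEs, each separately and as a composite.

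**The concern.** Two rules do not fit the definitions that they serve.

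First, the expedited rule selects by severity, whereas the sponsor's duty follows seriousness. A serious event that is not life-threatening can be a SUSAR and carries its own 15-day limit. Yet nothing in the protocol says how soon the site must send it. Because the sponsor's clock starts on receipt, delay at the site is neither limited nor counted.

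Second, every patient is in hospital at entry (4.1), so a hospitalisation criterion confined to prolonging a stay suits the index admission. SAEs are collected to three months, and after discharge the relevant hospital event is a new admission. The list does not contain it, but the surrounding text reads as if it did. Sites have to decide for themselves. The trial is open-label (10.2.3), so such decisions could differ by arm as well as by site.

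At stake are the speed of safety review for part of the SAEs, and the consistency of the SAE endpoint after discharge.

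**Working it through.** No arithmetic applies. The check sets the sections side by side.

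**A. Which SAEs have a site deadline?**

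- *Life-threatening event (9.1.2).* It corresponds to grade 4 in 9.1.5, so the 24-hour rule applies.
- *Death.* The scale has no fatal grade. The rule applies only if the site graded the event 4.
- *Prolonged stay, incapacity, birth defect, important medical event.* None of these implies grade 4, and 9.1.2 says outright that an important medical event need not be life-threatening. Rated below 4, such an event has no stated deadline.

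Of the six grounds, one matches grade 4 by definition. This describes the wording only. The grounds overlap, and the count says nothing about how many SAEs are affected.

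**B. Does another rule fill the gap?** Section 9.1.9 and the synopsis also require a report within 24 hours through the WHO route, but only for life-threatening reactions that are both serious and unexpected. That leaves out SAEs that are not life-threatening. Section 9.1.7 requires all SAEs to be reported, but it gives a collection window and no deadline.

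**C. What follows for the sponsor?** The 7- and 15-day limits run from receipt. For an SAE below grade 4, the time from site awareness to regulatory report is an unspecified site interval plus up to 15 days if the event is not fatal or life-threatening. Section 9.1.3 directs particular attention to renal function under Remdesivir. A serious renal event rated grade 3 is an example of an SAE without a site deadline.

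**D. Is new admission an SAE criterion?**

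- By the list in 9.1.2: no, only prolongation of a stay already under way.
- By the sentence on important medical events: yes, since it names requiring hospitalisation beside death and threat to life, as one of the outcomes that such an event may lack.
- By the elective exception: yes, since an exemption is needed only if admission otherwise counts.

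The section therefore supports both answers.

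**E. What follows for 10.5.3?** Take a non-elective readmission that meets no other ground.

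- *Graded 3 or 4:* recorded as an AE under 9.1.7 whichever answer the site chooses. Whether it counts as an SAE depends on the site. If severe AE in 10.5.3 means grade 3 or higher (an assumption), it still enters the composite.
- *Graded 1 or 2:* if the site follows the list, it is not an SAE and 9.1.7 does not call for it as an AE, apart from the provision for Remdesivir events during or shortly after administration. It is then absent from both the SAE endpoint and the composite.

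The SAE endpoint is thus exposed at any grade, and the composite mainly below grade 3.

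**F. Grade wording.** Section 9.1.7 names grades 3 and 4, while 9.1.1 and 9.1.8 name grade 3 only.

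**The case against.** A reader might infer that fatal and grade 3 serious events fall outside the rules on which the safety analysis relies. The protocol does not support that. Sections 9.1.2 and 9.1.7 require all SAEs to be recorded and reported through three months, whatever their grade, and 10.5.3 analyses death as an endpoint of its own. The grade 4 wording governs speed of submission, not what enters the database.

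A reader might also infer that readmissions are simply missing from the SAE endpoint. That is too strong. Many will qualify as life-threatening, incapacitating or important medical events, and the two sentences in 9.1.2 signal to sites that admission matters. What remains is inconsistent classification, with omission possible.

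Three further objections have weight:

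- Nothing prevents a site from giving a fatal event the highest grade, and many such events will have been life-threatening first. The gap for deaths is therefore limited to those not graded 4.
- Section 9.1.8 promises separate reporting guidelines to sites and 9.1.9 refers to SOP 9. Neither is shown, and either may add deadlines. Actual lateness is therefore not demonstrated. They would not, however, remove the restriction in 9.1.9 or the contradiction in 9.1.2.
- The grade wording has a coherent reading: 9.1.8 deals with grade 3, 9.1.9 with grade 4, and 9.1.7 gives the total. This is loose drafting and a minor point.

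**Conclusion.** Two defects stand on the protocol's own text. The 24-hour site deadline is stated only for grade 4 SAEs, so fatal events not graded 4 and SAEs below grade 4 have none in this document, although the sponsor must assess them all. And 9.1.2 contradicts itself on whether a new non-elective admission is serious.

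The first affects how promptly the Medical Monitor and the sponsor see part of the SAEs. The second affects how readmissions in the three-month window are counted in the SAE endpoint and, to a lesser extent, the composite. Neither touches the primary outcome, and neither prevents capture of fatal or grade 3 events.

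The size cannot be estimated, because the protocol gives no readmission rate, length of stay or distribution of SAE grades. The conclusion rests on the protocol text alone and assumes that the unseen site guidelines and SOP 9 do not already set wider deadlines. The change should be made: it is cheap, and the rules followed as written allow delay and inconsistent counts.

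**What to change.** 1. In 9.1.9, apply submission within 24 hours of site awareness to any SAE, regardless of grade. A separate fatal grade is then not needed for the deadline.
2. In 9.1.2, add inpatient hospitalisation or readmission to the list of seriousness criteria, and keep the exception for elective procedures.
3. As a minor point, align the grade wording in 9.1.1 and 9.1.8 with grades 3 and 4 in 9.1.7.
4. Check that the site reporting guidelines and SOP 9 agree with the amended text. Recruitment is already under way, so also state how admissions that occurred before the amendment are to be classified. Otherwise the SAE count would mix two definitions.

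The cost is a wording amendment, notice to sites and somewhat more expedited SAE reports. No treatment rule, sample size or efficacy analysis changes.

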9.2 Procedures in Case of Emergency

The investigator is responsible for assuring that there are procedures and expertise available to cope with emergencies during the study. The study is not blinded and code breaking procedures is therefore unnecessary.

9.3 Safety Committee

There will be two Data and Safety Monitoring Committees (DSMC), one global and one national. The global is detailed in the core protocol (Appendix 1) while the national DSMC will monitor the safety and evaluate the risk-benefit of the study interventions in the Norwegian patients. The national DSMC will consist of two clinicians and one statistician.

9.4 Protocol deviations

A protocol deviation handling plan will describe reporting procedures for important protocol deviations. Substantial overdosing should be reported within 24 hours in the WHO study website. As the protocol leaves the local doctor fully responsible for all decisions about patient care, including the possibility of discontinuing study medication if this is considered appropriate, the

only possible major protocol deviation would be substantial over-dosing with a study drug. If this happens, it should be reported within 24 hours on the study website. The DSMC chair will then decide whether this constitutes a sufficiently major protocol deviation for it to need to be forwarded promptly to the relevant national coordinator and to any relevant ethics committee

10 Statistical methods and data analysis

10.1 Determination of Sample Size

Recruitment will continue until the global core trial is concluded (Appendix 1). Assuming 5% all-cause in-hospital mortality in the standard of care arm and that 2% absolute risk difference is regarded a clinically meaningful difference, 2377 patients in each arm are required to conclude with benefit on a 2.5% two-sided significance level with 90% power. This calculation adjusts for multiple testing using Bonferroni correction. If even more proof is needed, 3412 patients in each arm are needed to conclude with benefit on a 1% two-sided significance level with 95% power. We will not be able to reach these numbers in this trial alone but will rely on the combined analyses of all participating trials in the global consortium.

In this trial we will therefore aim to show a difference in receipt of intensive care. Currently in Norway there are 70 patients in intensive care out of 268 (26%). With a minimum clinically important difference of 10% our goal is to randomize 406 patients in each group to be 90% certain to conclude with benefit on the 2.5% two-sided level.

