2.3 Study design

The NOR-SOLIDARITY study is an adaptive, randomized, open clinical multicentre trial to evaluate the safety and efficacy of possible therapeutic agents in hospitalized adult patients diagnosed with COVID-19. See the WHO COVID-19 core protocol (Appendix 1) for the core trial design. This multicentre add-on trial will follow the WHO core protocol version 10 dated 22.03.2020 but will add additional secondary and exploratory endpoints.

Adults (age ≥ 18 years) recently hospitalized, or already in hospital, with definite COVID and, in the view of the responsible doctor, no contra-indication to any of the study drugs will be randomly allocated between

- Local standard of care alone,
OR local standard of care plus
- Remdesivir (one intravenous loading dose, then daily infusions for altogether 10 days)

The primary objective of the trial is to investigate the effect of Remdesivir on all-cause in-hospital mortality compared to standard of care.

Patients will be followed daily during hospitalization, after 28 days by telephone/sms and then by an outpatient clinical visit after 3 months.

In the core protocol follow-up data are only collected at discharge. In this protocol subjects will additionally be assessed for efficacy and safety both during hospitalization and after hospitalization.

In addition to the global independent data and safety monitoring board (DSMB) as described in the core protocol, a national DSMB will monitor the safety and risk-benefit of the trial interventions in the Norwegian population.

[figure not shown]

Figure 2: The Investigational NOR-SOLIDARITY protocol

3 Objectives and endpoints

Objectives	Endpoints (Outcome measures)
Primary (in line with WHO core protocol)	
To investigate the effect of Remdesivir on all-cause in-hospital mortality compared to standard care.	All-cause in-hospital mortality
Secondary (in line with WHO core protocol)	
Assess the effect of Remdesivir on hospital duration, receipt of ventilation or intensive care, and to identify any serious adverse reactions.	During hospitalization 
 • Receipt of mechanical ventilation • Time to first receiving and duration of mechanical ventilation • Receipt of intensive care • Duration of intensive care • Occurrence of Suspected Unexpected Serious Adverse Reactions (SUSARs)
Secondary (as addition to the WHO core protocol)	

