Assess the effect of Remdesivir on 28 days mortality, viral clearance, kidney and myocardial failure, co-infections, organ dysfunction and health-related Quality of Life.	Assessed during hospitalization 
 • Viral clearance as assessed by SARS-CoV-2 PCR in oropharyngeal specimens during hospitalization • Occurrence of kidney failure (eGFR <40 mL/min) • Occurrence of myocardial involvement assessed by biochemical markers as well as echocardiography measuring left ventricular ejection fraction within the first week • Occurrence of co-infections (super infections with bacteria, fungi and other virus) Assessed after 28 days 
 • Overall survival • Patient reported respiratory health status by CAT (Chronic Obstructive Pulmonary Disease (COPD) assessment Test) score Assessed after 3 months 
 • Occurrence of systolic and diastolic cardiac dysfunction and level of remodelling assessed by echocardiography and biochemical markers • Occurrence of pulmonary dysfunction and level of fibrosis assessed by spirometry and thoracic CT scan • Health related quality of life assessed by the RAND 36-item Short Form Health Survey (SF-36) item scores and the 5-dimension EuroQol (EQ-5D) questionnaires index value.
Exploratory (as addition to the WHO protocol)	

Assess the effect of Remdesivir on biomarkers and its safety.	Biomarkers during hospitalization and after 3 months 
 • Inflammatory and anti-inflammatory mediators as assessed in serum and plasma • Markers of extracellular matrix remodelling • Markers of endothelial activation • Markers of platelet activation • Cellular immunity • Prognostic biosignatures (RNA) • Gut microbiota assessed by rectal swab • Pharmacokinetics during hospitalization • Adverse events during hospitalization
---	--

4 Study population

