4.1 Inclusion criteria (as described in WHO COVID 19 core protocol)

1. Adult patients, 18 years and above
2. Confirmed SARS-CoV-2 infection by PCR
3. Admitted to the hospital ward or the ICU
4. Subjects (or legally authorized representative) provide informed consent prior to initiation of the study
5. No anticipated transfer within 72 hours to a non-study hospital

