10.2 Randomization

10.2.1 Allocation- sequence generation

Eligible patients will be allocated in an equal ratio, using a computer randomization procedure. The allocation sequence will be prepared by an independent statistician appointed by the international steering group. The randomization procedure will accommodate availability of each treatment such that a patient cannot be allocated to an unavailable treatment. There will be no stratification of the allocation sequence, only simple randomization.

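### The 406 per arm is sized on a one-day share of patients in intensive care and not limited to patients outside ICU at randomisation, so the stated 90% power holds only under favourable assumptions

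*Protocol*

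**What the plan says.** Protocol section 10.1 accepts that mortality cannot be powered nationally and sizes this trial on intensive care instead. The control rate comes from "Currently in Norway there are 70 patients in intensive care out of 268 (26"%). The target follows: "With a minimum clinically important difference of 10% our goal is to randomize 406 patients in each group". The power claimed for that number is 90%, at a two-sided level of 2.5%. Section 10.4 uses the same 406 per arm as one of the triggers for analysis.

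Section 4.1 makes patients eligible if "Admitted to the hospital ward or the ICU". The synopsis records at entry whether a patient is already ventilated, and section 7.4.1 expects particular benefit in ICU patients, so these patients are an intended part of the population.

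Section 3 lists the endpoint, during hospitalisation, only as "Receipt of intensive care". Section 10.3 puts all randomised patients in the ITT set, and section 10.5.2 analyses secondary efficacy endpoints in the ITT and per-protocol sets. Section 10.5.1 analyses mortality separately by whether the patient was admitted directly to intensive care. Section 10.5.2 carries the primary method over to secondary variables only where it applies.

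**The concern.** A patient in ICU at randomisation has already received intensive care, and treatment cannot prevent that. If such patients count as events, they add equally to both arms and shrink the difference. If they are left out, fewer than 406 per arm remain. Section 10.1 allows for neither.

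The planning rate is also the wrong kind of quantity. A count of patients lying in ICU on one day is a prevalence. The design needs the incidence of new ICU admission after randomisation among patients not yet there. The documents do not show whether the snapshot over- or understates that incidence.

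At stake is the 90% power claimed for the one comparison that the national trial says it is sized to show.

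**Working it through.** **Inputs.** Control 26% (70/268 = 26.1%), reduction 10 points, two-sided level 2.5% and power 90% are from section 10.1. Equal allocation is from section 10.2.1 ("Eligible patients will be allocated in an equal ratio, using a computer randomization procedure"). The share b of randomised patients in ICU at entry is not in the documents; I assume 5%, 10% and 15%.

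**Step 1: reproduce 406.** Unpooled normal approximation:

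n = [0.26×0.74 + 0.16×0.84] × (2.2414 + 1.2816)² / 0.10² = 0.3268 × 12.411 / 0.01 = 405.6, rounded up to 406.

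The stated figure is reproduced exactly.

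**Step 2: power formula used below.** Power = Φ[(d − 2.2414×SE0)/SE1], where d is the difference, SE0 = √[2p̄(1−p̄)/n] and SE1 = √{[pC(1−pC) + pT(1−pT)]/n}. For 26% vs 16% and n = 406: SE0 = 0.02859, SE1 = 0.02837, power = Φ(1.266) = 89.7%.

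**Step 3: 26% and 16% are the rates among patients at risk.**
- Counted: control b + (1−b)×0.26, treated b + (1−b)×0.16, n = 406.
- Excluded: 0.26 vs 0.16, n = 406×(1−b).

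| b | Rates, counted | Power, counted | n at risk per arm | Power, excluded |
|---|---|---|---|---|
| 5% | 29.7% vs 20.2% | 81% | 386 | 88% |
| 10% | 33.4% vs 24.4% | 72% | 365 | 86% |
| 15% | 37.1% vs 28.6% | 63% | 345 | 84% |

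If the trial population matched the snapshot (b = 26%), these would be 46% and 78%.

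**Step 4: 26% is total receipt, including patients in ICU at entry.** The control rate among those at risk is q = (0.26−b)/(1−b). The planned relative effect, 0.16/0.26 = 0.615, acts on new admissions only.
- Counted: 0.26 vs b + (0.26−b)×0.615, n = 406.
- Excluded: q vs 0.615q, n = 406×(1−b).

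| b | Rates, counted | Power, counted | Rates, excluded | Power, excluded |
|---|---|---|---|---|
| 5% | 26% vs 17.9% | 71% | 22.1% vs 13.6% | 80% |
| 10% | 26% vs 19.8% | 44% | 17.8% vs 10.9% | 65% |
| 15% | 26% vs 21.8% | 20% | 12.9% vs 8.0% | 46% |

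**Step 5: when is 90% kept?** If patients at risk have control rate q, fall by a full 10 points and are analysed alone, power is 93%, 97% and 99.6% for b = 5%, 10% and 15%. The relative risks needed, (q−0.10)/q, are 0.55, 0.44 and 0.23, against 0.615 planned. If ICU-at-entry patients are counted and 26% is total receipt, a 10-point overall difference needs a relative risk among the rest of 1 − 0.10/(0.26−b) = 0.52, 0.375 and 0.09. It is impossible once b exceeds 16%.

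**The case against.** **Nothing says that ICU-at-entry patients count as events.** This is correct. A reader might infer it from the all-randomised analysis set and the bare endpoint label, but that is an inference from silence. Some text points the other way: the synopsis speaks of time to first ventilation or intensive care, and sections 10.5.1 and 10.5.2 leave room for a split by ICU at entry. The SAP may settle the derivation. This does not rescue section 10.1: excluding these patients leaves fewer than 406 per arm at risk, and under the planned relative effect power is below 90% either way.

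**The loss depends on assumptions.** Also correct. The share b is not given, the protocol states an absolute rather than a relative effect, and the 71% to 20% range is the harshest of the cases shown. Step 5 shows a case where power exceeds 90%. A higher incidence of new ICU admission than 26% would also raise power; the documents neither support nor exclude that.

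**The consequences are limited.** Counting such patients in both randomised arms dilutes the effect without inflating type I error. Mortality is left to the combined global analysis, and section 12 concedes that enrolment may be too small. That limits the consequence, but the 90% remains a stated figure that needs a basis.

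**Conclusion.** The concern holds in a limited form. The 406 is arithmetically right for 26% vs 16%; the weakness is the assumption beneath it. Taking 26% as either the at-risk rate or the total rate, 90% power requires almost nobody in ICU at entry or a relative effect in patients at risk larger than 16/26. With an assumed 5% to 15% in ICU at entry, power is about 81% to 63% (counted) or 88% to 84% (excluded) on the first reading, and about 71% to 20% or 80% to 46% on the second.

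Two stronger conclusions are not supported. The documents do not show that power is as low as 20% to 71%, because that needs both the second reading and the counting of ICU-at-entry patients. Nor does the kidney endpoint, "Occurrence of kidney failure (eGFR <40 mL/min"), share a power error. It has no baseline condition, and section 4.2 has no renal exclusion, so its definition is loose. But it does not size the trial and no power is claimed for it.

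**What to change.** - In section 3, define the endpoint as new receipt of intensive care after randomisation, analysed in patients not in ICU at randomisation. Treat receipt of ventilation likewise, in patients not ventilated at entry.
- Keep patients in ICU at entry in the mortality analysis.
- In section 10.1, replace the snapshot with an incidence of new ICU admission among patients at risk. State the assumed share in ICU at entry and give, as a range, the power that 406 randomised per arm provides.
- As a minor definition point, count kidney failure in patients with baseline eGFR of 40 or more.

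**Cost.** This is protocol wording, with matching SAP text. Severity at entry is already foreseen in the synopsis and sections 4.4 and 10.5.1, but ICU status should be taken at randomisation. The downside is a less favourable stated power. Keeping 90% instead would need more patients: with the pooled formula (410 per arm at b = 0) and exclusion, 432, 456 or 483 randomised per arm for b = 5%, 10% or 15% on the first reading, and 529, 724 or 1102 on the second.
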